## RESEARCH PROTOCOL AND STATISTICAL ANALYSIS PLAN

TITLE	The Effect of Balance Bike Training on Balance, Physical Activity Levels, and Participation in Children and Youth with Down Syndrome: A Pilot Study
ABSTRACT	
Background: Children with Down syndrome (DS) present with hypotonia, impaired balance and poor gross motor proficiency which lead to difficulty learning new motor skills, decreased engagement in physical activity, and limited participation in home, school, and community activities. Bicycle riding is a popular childhood activity with multiple health benefits; however, children with DS often have difficulty learning to ride a standard two-wheel bike. Purpose: The purpose of this pilot study is to determine the effectiveness of the Strider “Learn to Ride” intervention when used to teach children with DS to ride a two-wheel balance bike. Additional purposes include examining the immediate effects of the five-day “Learn to Ride” intervention on the balance of children with DS and the long-term effects of completion of the intervention on the participation and physical activity levels of children with DS. Methods: An estimated 20 children between the ages of 5 and 17 years old will be recruited to participate in the quasi-experimental, pre-post-test group design study. The participants will complete the five-day Strider “Learn to Ride” intervention under the instruction of a pediatric physical therapist. The immediate effects of the intervention on distance cycled and balance, using the Pediatric Balance Scale (PBS), will be assessed. Participation and physical activity levels will be assessed at long term follow-up using the Participation and Environment Measure for Children and Youth (PEM-CY) and a parent-report questionnaire.

BACKGROUND	
Bicycle riding is a popular childhood activity; however, individuals with Down syndrome (DS) often have difficulty mastering this skill. Down syndrome, a common chromosomal disorder identified in approximately 1 in 700 live births, carries the certainty of developmental delay and altered gross motor movement proficiency. Individuals with DS present with cerebellar hypoplasia which contributes to delayed motor skills, problems with axial control, and impaired coordination. Additionally, a reported 58% of children and adolescents with DS do not meet the Office of Disease Prevention and Health Promotion’s PA guidelines, and evidence suggests that PA levels continue to decrease as children move into adolescence. Additional characteristics of children with DS contributing to physical inactivity and difficulty learning to ride two-wheel bikes include cognitive impairments, hypotonia, balance impairments, and reduced exercise capacity. Societal and environmental barriers to PA, including limited opportunities for participation in inclusive sports and high costs of adaptive equipment also contribute to

	
low fitness levels of this population. Identification of enjoyable, sustainable, accessible, and effective forms of PA for this population is necessary in order to promote improved overall health and participation across the lifespan. Bicycle riding has been identified as a source of moderate to vigorous PA for children and adolescents and is a noncompetitive, highly accessible activity that can be enjoyed across the lifespan. However, research examining bike riding as an enjoyable and effective PA intervention for adolescents with developmental disabilities, particularly DS, is limited. One study examined the benefits of children with DS learning to ride an adaptive two-wheel bicycle. The children participated in “Lose the Training Wheels”, an intensive, five-day program aimed at teaching the skill of riding a two-wheel bike independently. Specially designed two-wheel adaptive bikes were used for initial training. The bikes were modified to include a push handle on the back, to be used by the instructor, and rear roller wheels to increase the bike’s base of support. Forty-four percent of the participants were unable to learn to ride a two-wheel bike during the training period. However, children who did complete the training program decreased their time spent in sedentary behavior by 75 minutes per day, indicating that new motor skill development might positively impact PA levels for up to 12 months following the initial intervention period. A similar study also examined the effectiveness of the “Lose the Training Wheels” program, previously described, for children and adolescents with DS and Autism Spectrum Disorder. The results indicated that 61% of children with DS continued to ride their bike at home after the intervention period ended, supporting transfer of an enjoyable PA to the natural environment. However, the adaptive bikes used for the “Lose the Training Wheels” program are specially made and not commercially available, making widespread access to this intervention difficult. Strider Bikes, a brand of commercially available balance bikes, are specifically designed to be lightweight, easy to handle, and safe for use with children with disabilities. One study using Strider bikes reported that children with autism spectrum disorder demonstrated significant improvements in postural control following completion of 15 minutes of riding, three days per week for five weeks. However, there is currently no research available that has utilized Strider bikes with youth with DS. In order to impact a large population of children with DS and create lasting, positive outcomes, a relatively inexpensive, commercially available adaptive bike and effective instructional intervention must be identified.

PURPOSE	The purpose of this pilot study is to determine the effectiveness of the Strider “Learn to Ride” intervention on the balance of children with Down syndrome and the long-term effects of completion of

	
the intervention on the participation and physical activity levels of children with Down syndrome. Our central hypothesis is that successful completion of the Strider “Learn to Ride” intervention will provide children with Down syndrome the ability to ride a two-wheel balance bike safely and independently. We also hypothesize that balance biking will be a sustainable activity that has the potential to greatly increase the functional balance, participation, and physical activity levels of youth with Down syndrome because we propose riding Strider bikes to be enjoyable and motivating for this population.

SPECIFIC AIM(S)	
Page 4 of 74/5/2019 Specific Aim(s) We plan to test our central hypothesis and meet our overall objective for this project by pursuing the following specific aims: 1. Determine the ability of youth with DS to learn to ride a Strider balance bike, within one week, utilizing the Strider “Learn to Ride” curriculum. Our working hypothesis is that youth with DS who complete the five “Learn to Ride” classes will be able to successfully and safely ride their Strider bike 100’ or more without loss of balance. 2. Determine the efficacy of balance biking on improving balance in youth with DS, as measured by the Pediatric Balance Scale (PBS). Our working hypothesis that balance will be improved in youth with DS who complete the balance biking intervention because biking is an enjoyable childhood PA that requires high levels of postural control. 3. Determine the long-term sustainability of balance biking for youth with DS, as estimated by a 3-, 6-, 9-, and 12-month follow up surveys. Our working hypothesis here is that balance biking will be a sustainable form of PA for individuals with DS that can be continued throughout the lifespan, leading to increased PA levels and decreased time spent engaged in sedentary behaviors. 4. Determine the impact of long-term participation in balance biking on home, school, and community participation levels, as measured by the Participation and Environment Measure for Children and Youth (PEM-CY). Our working hypothesis that long-term involvement in a balance biking program will lead to increased participation in home, school, and community environments.

STUDY DESIGN	
The proposed pilot study is a pre-post-test design with each participant serving as his or her own control. The proposed study design will provide preliminary data towards answering the hypothesis and specific aims. Children ages 5-17 years old with a diagnosis of Down syndrome will be recruited to participate from pediatric therapy clinics, schools, and the Central Mississippi Down Syndrome Association. Each participant will be provided with a Strider balance bike to use for the intervention. On the first day of the intervention, each participant will complete the Pediatric Balance scale and the distance that each child can cycle will be recorded. Participants’ parents will be asked to complete the Participation and Environment Measure for Children

	and Youth (PEM-CY) and the PROMIS physical activity questionnaire on the first day of the intervention. Each participant will complete the 5-day Strider Learn to Ride Intervention under the supervision of a physical therapist. On the last day, each child will be reassessed with the Pediatric Balance Scale and the distance that each participant can cycle will again be recorded. Participants' caregivers will be contacted by mail from the PI to complete follow up outcome measures (PEM-CY and PROMIS questionnaire) at 3-and6-months.
INCLUSION CRITERIA	To be included in the study, the individuals must 1) be between the ages of 5 and 17 years old with a diagnosis of Down syndrome, 2) have the core strength and balance necessary to maintain sitting on a two-wheel bike with their feet on the ground, and 3) be able to follow simple commands.
EXCLUSION CRITERIA	The exclusion criteria for the study are 1) significant cardiovascular event or illness in the past 6 months and 2) another medical diagnosis, besides Down syndrome, that would limit participation in the biking intervention.
NUMBER OF SUBJECTS	Approximately 10 participants will be recruited to participate in the pilot study, based on the recommended number of participants for each Strider "Learn to Ride" intervention.
OUTCOME MEASURES	Outcome measures used will include the Pediatric Balance Scale (PBS), distance cycled, Participation and Environment Measure for Children and Youth (PEM-CY), and PROMIS questionnaire. The PBS is a valid, 14-item assessment, developed based on the Berg Balance Scale. The PBS is a criterion-based measure, with each item scored on a 0-4 scale. Distance cycled will be measured based on the longest straight-line distance, out of three trials, that the participant is able to safely and independently propel their Strider bike. The PEM-CY is a participation level outcome measure used to assess a child's engagement in activities in the home, school, and community environments. The PEM-CY is a valid and reliable measure and is completed by parent/caregiver report, making it appropriate to use with children with Down syndrome. The final outcome measure, a parent report PROMIS questionnaire to assess PA levels of participants, will also be used. Long-term follow up at 3-and 6 months, through mail, will be completed to assess long-term changes in participation and physical activity levels as well as the sustainability of the Strider bike intervention for this population.
STUDY ENDPOINTS	All outcomes measures will be administered on the first day of the intervention to collect pre-intervention data. Upon completion of the five-day "Learn to Ride" intervention, the Pediatric Balance Scale and distance cycled will again be administered for post-intervention data. The Participation and Environment Measure for Children and Youth and the PROMIS physical activity questionnaire will be administered, my mail, to each participants' caregiver/parent at 3-and-6-months following completion of the

	
intervention to assess long-term outcomes associated with the intervention.

STATISTICAL METHODOLOGY	
IMB SPSS Statistics will be used to analyze all data. Dependent t-tests will be used to analyze pre-and post-test scores of the Pediatric Balance Scale, Participation and Environment Measure for Children and Youth, and distance cycled. If assumptions are not met, a Wilcoxon Signed Ranks test will be used to analyze the data.

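### The hypothesis says children will ride safely, but the plan keeps only each child's best supervised straight-line run and records no falls or injuries

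*Combined protocol and SAP*

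**What the plan says.** The combined protocol and SAP puts safe riding into its main claim twice. Under Purpose, the central hypothesis is that completing the programme will give children "the ability to ride a two-wheel balance bike safely and independently". Under Specific Aim(s), the working hypothesis of Aim 1 is that children who complete the five classes "will be able to successfully and safely ride their Strider bike 100’ or more without loss of balance".

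The Outcome Measures section is complete and lists four measures: "Outcome measures used will include the Pediatric Balance Scale (PBS), distance cycled, Participation and Environment Measure for Children and Youth (PEM-CY), and PROMIS questionnaire". Only distance cycled refers to safety. It is "the longest straight-line distance, out of three trials", "that the participant is able to safely and independently propel their Strider bike".

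Study Design states: "Each participant will complete the 5-day Strider Learn to Ride Intervention under the supervision of a physical therapist". It does not say that the therapist records falls or injuries. Mailed follow-up at 3 and 6 months consists of the participation and physical activity questionnaires. Statistical Methodology plans paired t-tests, or Wilcoxon signed-rank tests, on the balance score, the participation measure and distance. It plans no summary of falls or injuries, and no estimate of how many children reach 100 feet.

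**The concern.** Safety is half of what the hypothesis asserts about riding, yet the stored result is a single distance per child at each assessment. Three things are lost.

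- **The judgement itself.** Neither *safely* nor *loss of balance* is defined, and the decision that a run was safe is not recorded separately from the distance.
- **The other two trials.** Keeping the longest run hides whatever happened in the rest.
- **The classes.** Whatever happens during five days of practice is captured by no listed outcome.

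The Background describes these children as having impaired balance, hypotonia and impaired coordination, and says that no earlier research has used these bikes with youth with Down syndrome. A first count of falls is therefore among the more useful things this pilot could pass to a later study. It cannot be reliably reconstructed once the classes are over.

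**Working it through.** The documents give no event rate, and no alpha, power or effect size, so there is no figure of the plan's own to reproduce. The check has two parts.

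**1. What the distance score can distinguish**

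Take two children assessed on the last day. One rides 100 feet cleanly in all three trials. The other falls in two trials and rides 100 feet cleanly in the third. The longest safe distance is 100 feet for both, so the dataset cannot tell them apart.

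As an illustration, assume that the three trials are independent and that each has probability q of a fall. The chance of at least one clean run is 1 − q³.

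| Assumed q | 1 − q³ |
|---|---|
| 0.30 | 1 − 0.027 = 97.3% |
| 0.50 | 1 − 0.125 = 87.5% |
| 0.70 | 1 − 0.343 = 65.7% |

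The values of q are assumptions. They show that a child who falls in half of all runs would usually still have a clean run to score.

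The plan also does not say how to score a trial that ends in a fall: up to the fall, as zero, or not at all. On the first reading, the longest distance could itself come from a run that ended in a fall.

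**2. What could be said if events were counted**

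The sample size is about 10 under Number of Subjects and an estimated 20 in the Abstract, so both are used. With no affected child among n, the exact upper limit for the per-child risk is 1 − 0.025^(1/n) for a two-sided 95% interval, and 1 − 0.05^(1/n) for a one-sided 95% bound.

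| n | Two-sided 95% upper limit | One-sided 95% upper limit |
|---|---|---|
| 10 | 1 − 0.025^(1/10) = 30.8% | 1 − 0.05^(1/10) = 25.9% |
| 20 | 1 − 0.025^(1/20) = 16.8% | 1 − 0.05^(1/20) = 13.9% |

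The same arithmetic applies to Aim 1. If every child rode 100 feet cleanly, the two-sided lower limit for the success proportion would be 100 − 30.8 = 69.2% at n = 10 and 100 − 16.8 = 83.2% at n = 20.

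The chance of seeing at least one affected child is 1 − (1 − p)^n, where p is an assumed per-child risk.

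| Assumed p | n = 10 | n = 20 |
|---|---|---|
| 5% | 40% | 64% |
| 10% | 65% | 88% |
| 20% | 89% | 99% |

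A tally would thus probably pick up a fairly common problem, but could not rule out a less common one. These limits describe what the pilot could say after the fix. They do not measure the present gap, which is that no such figure can be given at all.

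**The case against.** A reader might go further and infer that the study has no data on safe riding and cannot speak to its central hypothesis. The documents do not support that. The distance outcome admits only distance ridden safely and independently, which repeats the hypothesis's own terms, and Aim 1 adds a 100-foot threshold without loss of balance. That is evidence, though limited to a supervised straight-line test and resting on an undefined judgement.

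The hypothesis is also about ability after completing the programme. Best of three is a reasonable way to measure ability, and falls during the classes happen while the skill is still being learned. They bear on how safe the training is, which the hypothesis does not claim. This objection stands, and it is why class falls should be reported separately.

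Nor do the documents commit the study to a general safety conclusion. Study Design promises only preliminary data. The concern is what the hypothesis's wording invites, not a claim already made.

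Finally, logging while teaching a group of about 10 takes some attention, and a sample this small cannot establish safety. Both points are fair. Neither removes the reason to record the events, because without a count not even a wide limit can be given.

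**Conclusion.** The point holds in a limited form. As planned, the study can show that a child managed at least one safe run on a supervised straight-line test, as judged by the assessor. It cannot show how often children fell in that test, whether they fell or were hurt in the classes, or that they ride safely in general.

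With events counted and none seen, the two-sided 95% upper limit would still be about 31% of children at n = 10 and about 17% at n = 20. These limits assume one yes-or-no result per child and independence between children.

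The analyses of balance, participation and physical activity are unaffected. This is an inexpensive improvement that should be made before the first class, because the information cannot be reliably recovered later.

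**What to change.** In Outcome Measures:

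1. State what counts as a fall and what counts as a loss of balance, including whether recovering by putting a foot down counts.
2. For each of the three distance trials, at both assessments, have the supervising therapist record the distance reached before any such event and whether one occurred. The longest distance can remain the score.
3. Tally falls and injuries per child in each of the five classes.

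In Statistical Methodology, add a descriptive report of:

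- the number of children who ride 100 feet or more without loss of balance after the intervention, with an exact 95% confidence interval;
- the number with any fall or injury in the post-intervention trials, with an exact 95% confidence interval;
- falls and injuries in the classes, reported separately as safety of the training.

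Limit any conclusion about riding safely to these figures and to the supervised setting.

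The cost is a short tally sheet per class and per distance test, some of the therapist's attention while teaching, and a more modest safety statement. It needs no extra participants or visits and does not change the intervention.

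### Aim 1 asks about all youth with DS but applies its 100-foot criterion only to those who complete five classes; a completer-only rate would probably overstate success if children stop early because they cannot manage the bike

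*Combined protocol and SAP*

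**What the plan says.** Under Specific Aim(s), the question in Aim 1 is broad: "Determine the ability of youth with DS to learn to ride a Strider balance bike, within one week". The working hypothesis that follows is narrower. It concerns "youth with DS who complete the five “Learn to Ride” classes", and success is that they can "ride their Strider bike 100’ or more without loss of balance". The central hypothesis under Purpose has the same condition: "successful completion of the Strider “Learn to Ride” intervention will provide children with Down syndrome the ability to ride".

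Study Design takes full attendance for granted: "Each participant will complete the 5-day Strider Learn to Ride Intervention under the supervision of a physical therapist". It then says: "On the last day, each child will be reassessed with the Pediatric Balance Scale". Distance cycled is recorded again on that same day, and Study Endpoints likewise places the post-test after the five days are complete. No assessment is described for a child who has stopped by then.

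Statistical Methodology analyses distance cycled by a dependent t-test, or by the Wilcoxon signed-ranks test if assumptions fail. It gives no proportion reaching 100 feet, no denominator, no analysis set and no rule for missing post-tests. No dropout rate is given anywhere.

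**The concern.** The aim and the hypothesis that is meant to answer it refer to different groups. Aim 1 asks how often youth with DS learn within a week. The hypothesis asks how often those who stay to the end can ride. A child who gives up because the bike is too hard is a failure under the first question and is absent from the second.

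The 100-foot criterion is a yes/no result for each child, so reporting it needs a denominator, and completers are the only group to which the plan attaches it. With about 10 children, each one who leaves can move the result by up to about 10 percentage points. A reader would naturally take the reported figure as the answer to the broad question.

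**Working it through.** The plan states no learn-to-ride rate, target proportion or dropout rate, so there is no figure to reproduce. The check has two parts.

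**1. How the text treats each kind of child**

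| Child | Covered by the Aim 1 question? | Covered by the Aim 1 hypothesis? | In the paired test of distance? |
|---|---|---|---|
| Completes all five classes | Yes | Yes | Yes |
| Misses a class, attends the last day | Yes | Not as worded | Yes |
| Stops before the last day | Yes | No | No, because there is no post-test value |

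The third row follows from the method: both planned tests use within-child differences, so a child with only a day-1 distance contributes nothing.

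**2. Size of the effect on a success rate**

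Let d be the share of starters who stop, p_c the success rate in completers, and p_s the rate that stoppers would show if assessed.

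- Rate among all starters = (1 − d) × p_c + d × p_s
- Completer rate minus starter rate = d × (p_c − p_s)

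The gap is zero if d = 0 or p_s = p_c, positive if stoppers ride less well, and negative if they ride better.

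Illustration with assumed counts: 10 start (the figure in Number of Subjects), 2 stop, and 7 of the 8 finishers ride 100 feet. Intervals are exact (Clopper-Pearson) 95%.

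- Completers: 7/8 = 87.5% (47.3% to 99.7%)
- All starters, stoppers counted as not successful: 7/10 = 70% (34.8% to 93.3%)
- All starters, stoppers counted as successful: (7 + 2)/10 = 90% (55.5% to 99.7%)
- Gap if no stopper could ride: 0.2 × (0.875 − 0) = 17.5 points
- Gap if both could ride: 0.2 × (0.875 − 1) = −2.5 points

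The Abstract gives an estimated 20 children instead of about 10. The same shares there (4 stop, 14 of 16 finishers succeed) give 14/16 = 87.5% (61.7% to 98.4%), 14/20 = 70% (45.7% to 88.1%), and an upper bound of 18/20 = 90% (68.3% to 98.8%).

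Range of the gap when no stopper could ride, d × p_c:

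| Share stopping (assumed) | p_c = 80% | p_c = 100% |
|---|---|---|
| 0% | 0 | 0 |
| 10% | 8 points | 10 points |
| 20% | 16 points | 20 points |
| 30% | 24 points | 30 points |

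**The case against.** Several points on the other side stand.

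- **No defined rate.** A reader might infer that the plan has a rule removing early stoppers from a denominator. It does not: the completer wording is in a hypothesis, and the statistical section defines no success proportion. Study Design also says every child is reassessed. But that sentence follows one that assumes every child completes, so it does not say what happens when one does not.
- **Direction is conditional.** A reader might infer that the bias must favour the programme. It needs children to stop, and stoppers to be less able to ride than completers. The documents give no attrition figures or reasons for stopping, and a child may stop for reasons unrelated to riding. Upward is nevertheless the likelier direction, because difficulty with the bike is an obvious reason to leave.
- **The cited programme is not a benchmark.** Background reports that "Forty-four percent of the participants were unable to learn to ride a two-wheel bike during the training period" in an earlier five-day programme. It is tempting to set a completer rate against the implied 100% − 44% = 56%. The documents do not plan that comparison, and the earlier programme used specially modified bikes. The apparent contrast also depends on the counts chosen. With 14 of 16 finishers succeeding out of 20 starters, only the completer interval lies above 56%. In the example with 10 starters, both intervals include it.
- **Completer success is a coherent question.** For a small pilot, the effect of the full course is worth reporting. It is just not the question that Aim 1 asks.

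**Conclusion.** The point holds as a mismatch between the Aim 1 question and the group its hypothesis judges, with no rule for children who stop early. If a completer-only rate is reported, it would probably overstate success among all who start, provided some children stop because they cannot manage the bike. In the 10-child example the difference is 17.5 points. With 10% to 30% stopping, completer success of 80% to 100% and no stopper able to ride, it is 8 to 30 points. It is zero if nobody stops, and zero or negative if stoppers ride as well as or better than completers. All stopping shares and success rates here are assumptions. The documents show neither that early stopping will occur nor its direction of effect, so this is a risk to be closed in advance and not a demonstrated bias.

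**What to change.** In Aim 1 and Statistical Methodology:

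1. Define the primary Aim 1 result as the proportion of all enrolled children who start class 1 that ride 100 feet or more without loss of balance on the last day, with an exact 95% CI.
2. Count a child with no last-day assessment as not successful. Beside it, show the bound with such children counted as successful.
3. Report the completer rate as secondary, with the number who stopped and the reasons if these are recorded.
4. Report how many children already rode 100 feet on day 1, since they cannot be said to have learned during the week.
5. Reconcile the planned number of children (about 10 in Number of Subjects, an estimated 20 in the Abstract), because it sets the denominator.

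The main result uses the day-1 and last-day distances that the plan already collects. Reasons for stopping are not among the data the plan lists, so recording them would be a small addition. The cost is that the reported rate may be less favourable. Counting unrelated absences as failures is also conservative, and the bound in step 2 shows how much that matters.

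### Aim 1 sets a 100-foot criterion for each child, but distance is analysed only as pre-post change, so the planned test does not answer the first aim

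*Combined protocol and SAP*

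**What the plan says.** Under Specific Aim(s), Aim 1 is to determine whether youth with Down syndrome can learn to ride the balance bike within one week. Its working hypothesis is that those who complete the five classes "will be able to successfully and safely ride their Strider bike 100’ or more without loss of balance". The central hypothesis under Purpose also concerns the ability to ride. The Abstract gives the study's purpose as the effectiveness of the programme "when used to teach children with DS to ride a two-wheel balance bike".

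Outcome Measures defines distance cycled as the "longest straight-line distance, out of three trials, that the participant is able to safely and independently propel their Strider bike". Study Design has it recorded on the first day, and on the last day "the distance that each participant can cycle will again be recorded".

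Statistical Methodology assigns dependent t-tests to the pre- and "post-test scores of the Pediatric Balance Scale, Participation and Environment Measure for Children and Youth, and distance cycled". The fallback is: "If assumptions are not met, a Wilcoxon Signed Ranks test will be used to analyze the data". No other analysis of distance is given.

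**The concern.** Aim 1 asks how many children can do something after training. The planned test asks whether average distance rose. A child can improve and still fall short of 100 feet, and a few children can pass 100 feet without producing a significant change in the group. No rule links the test result to Aim 1.

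Followed as written, the plan gives a p-value for change on the first aim and no estimate of how many children learned to ride. The Background section itself reports an earlier bicycle programme by the share of participants who did not learn (44%). Bike and programme differ, so that figure is context only, but a reader will look for the matching proportion here and not find it.

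If the count is added after the data are in, the choice of denominator and the treatment of children who already ride 100 feet on day 1 will be made with the results in view.

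**Working it through.** The documents give no effect size, SD, target proportion or power for distance, so there is no figure to reproduce. The check is whether the planned test can stand in for the criterion.

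**Text side by side**

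| Item | Aim 1 hypothesis | Outcome and statistical sections |
|---|---|---|
| Quantity | met or not met, per child | distance, best of three trials |
| Time | after the five classes | first day against last day |
| Threshold | 100 feet | none |
| Summary | share of children (implied) | t-test or Wilcoxon test of change |
| Population | completers | not stated |
| Condition | no loss of balance | safe and independent propulsion |

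**Can the two disagree?** All distances below are assumed, in feet, for n = 10. Day 1 in both sets: 20, 35, 10, 50, 25, 40, 15, 30, 45, 20.

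*Set A*, last day: 45, 50, 30, 80, 40, 75, 35, 45, 85, 50.
- Gains: 25, 15, 20, 30, 15, 35, 20, 15, 40, 30. The sum is 245, the mean 24.5 and the SD 8.96.
- Paired t = mean / (SD/√n) = 24.5 / (8.96/√10) = 24.5 / 2.83 = 8.65 on 9 df, p = 0.00001.
- Wilcoxon: all ten gains are positive, so the exact p = 2/2^10 = 0.002 (0.005 by normal approximation).
- Children at 100 feet or more: 0/10. Exact 95% upper limit = 1 − 0.025^(1/10) = 0.308, so 0 to 31%.

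*Set B*, last day: 110, 25, 5, 120, 20, 30, 105, 20, 40, 15.
- Gains: 90, −10, −5, 70, −5, −10, 90, −10, −5, −5. The sum is 200, the mean 20.0 and the SD 44.1.
- Paired t = 20.0 / (44.1/√10) = 20.0 / 13.94 = 1.43 on 9 df, p = 0.19.
- Wilcoxon: rank sums 27 and 28, p = 0.97 (0.96 to 1.0 depending on how ties are handled).
- Children at 100 feet or more: 3/10, exact 95% CI 7 to 65%.

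Set A has a strong result on the planned test and no child meeting the criterion. Set B has no significant change and three children meeting it.

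**Precision of the matching analysis.** The documents give two sizes: "Approximately 10 participants will be recruited to participate in the pilot study" (Number of Subjects) and "An estimated 20 children between the ages of 5 and 17 years old will be recruited" (Abstract). For x successes in n, the Clopper-Pearson limits are the 2.5% quantile of Beta(x, n−x+1) and the 97.5% quantile of Beta(x+1, n−x). With an assumed 80% success rate:
- 8/10: 44.4 to 97.5%
- 16/20: 56.3 to 94.3%

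**Denominator.** Assume one of 10 enrolled children has no last-day trial and eight succeed. Among completers this is 8/9 = 89% (52 to 100%). Among all enrolled it is 8/10 = 80% (44 to 97%).

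**The case against.** The strongest reply is that learning within a week is itself a question about change, so comparing day-1 with last-day distance bears on Aim 1; the 100-foot figure sits in the working hypothesis, not in the aim's first sentence. This is a small pilot that claims only preliminary data, and anyone can count the children at 100 feet from what is recorded. Set B is also contrived: seven of ten children ride less far after training, and its gains are so far from normal that the plan's own fallback would replace the t-test.

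Part of this stands. The paired test gives related evidence and should be kept. Set B shows only that the second kind of conflict is possible, and Set A makes the main point alone. The completer rule, the day-1 riders, the loss-of-balance wording and the course length are clarifications, not separate defects. No child may ride 100 feet on day 1, and safe, independent propulsion may be meant to exclude a loss of balance.

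The main point is unaffected. The 100-foot criterion is the protocol's own definition of success for Aim 1, and no planned analysis addresses it. Pilot status is no defence, because a count with an interval needs no power. Whether loss of balance ends a trial has to be settled before testing; it cannot be recovered from a recorded distance.

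**Conclusion.** The concern holds and should be fixed. The plan sets a criterion for each child and then tests average change, which can be highly significant with 0 of 10 children meeting the criterion. That conclusion rests on the text and on the nature of the two quantities. The data sets are assumed and say nothing about how often a conflict would occur. The gap affects the first aim and the central hypothesis, but it lies in the analysis plan: the distances needed are already to be collected.

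**What to change.** In Statistical Methodology, name as the Aim 1 analysis the number and proportion of children who ride 100 feet or more without loss of balance on the last day, with an exact (Clopper-Pearson) 95% CI. Then:

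- Report it for completers of the five classes, which is the stated hypothesis, and for all enrolled children with a missing last-day trial counted as not successful.
- Show separately any child already at 100 feet or more on day 1.
- Add the loss-of-balance condition to the distance definition in Outcome Measures, and tell assessors when a trial ends.
- Confirm that the straight test course is at least 100 feet long, since the documents give no length.
- Keep the paired t-test or Wilcoxon test of distance as supportive.
- Reconcile the two sample sizes, because the width of the interval depends on them.

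The cost is a few sentences, one phrase in a definition and one assessor instruction, with no new visit or measure. The drawbacks are the wide interval at either size and an all-enrolled rate that may be lower than the completer rate. With 10 to 20 children this is estimation, and no hypothesis test of the proportion is needed.
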